3.3 AEFI Measurement

This study will employ the platform used by the Canadian National Vaccine Safety Network (CANVAS) to conduct active surveillance during the first four weeks of the seasonal influenza vaccine campaign to assess pharmacy-based recruitment of vaccine recipients into an AEFI surveillance program (De Serres, 2012; Bettinger, 2015). Patients receiving an influenza vaccine at a pharmacy in one of the study communities will be eligible to participate in a specific survey of adverse events experienced during the first 7 days following vaccination. In the intervention communities, vaccine recipients will be given an information sheet describing the survey and the CANVAS registration form. Participants will be asked to complete the registration form or to register online by providing their first name, vaccine received and date of vaccination, email address, and telephone number. In the control communities, recruitment will be passive (e.g., posters and information sheets will be displayed) and potential participants will be required to register online. Only individuals ≥18 years of age who received the seasonal influenza vaccine and who are English or French-speaking will be invited to register and complete the survey.

The AEFI survey will be emailed to registered participants on day 8 post-vaccination. An automatic reminder will be sent on day 11 post-vaccination to those who have not completed the survey. The survey will collect information regarding vaccine provider, vaccine product, participant age and gender. Respondents will be asked to indicate if they experienced a health event that prevented their daily activities or led them to seek medical attention. Those who report symptoms severe enough to prevent daily activities or require medical attention will be asked details about the onset, duration, and type of

ROMEO File #: 1021559

symptoms experienced within the first 7 days post-vaccination. Participants reporting events severe enough to require medical attention will be contacted by a trained study nurse within 3-5 days. Events will be reported to public health as per local guidelines.

Participants who register for the AEFI survey will be registered in CANVAS as well. As such, they will be invited to complete the "control survey" which aims to determine the underlying rate of illness in the population that occurs irrespective of vaccination, known as the "background event rate". To collect information on the background rate of health events participants will receive a second email survey about two weeks before the start of the next seasonal influenza vaccination campaign (e.g. 2016 participants will receive an email in the fall of 2017 and 2017 participants will receive an email in the fall of 2018). That survey will collect data about the occurrence of clinical problems in the prior 7 days. A reminder email will be sent 7 days before the survey to mark the start of the 7-day monitoring period for participants.

RedCap[™] software will be used. The database will be accessible through a secure web application with personal passwords for research staff. All participant information will be stored in RedCap[™] and contact information will only be available to authorized staff (e.g., study nurse). The number of influenza vaccine recipients in each community will be ascertained from pharmacy databases.

The proportions of influenza vaccine recipients who registered for and completed the online AEFI survey will be compared among intervention and control communities. Frequencies of severe AEFI, and of AEFI requiring medical attention will be determined. The frequency of severe adverse events will be determined by influenza vaccine type [e.g., quadrivalent inactivated influenza vaccine (QIV), TIV] and by season (i.e., 2016-17 and 2017-18).

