- 2. To determine pre- and post-intervention knowledge, attitudes, beliefs and behaviours (KABB) of target adults, pharmacists, physicians, and vaccine providing nurses.

Secondary Objectives:

- 1. To assess the impact of various funding models on vaccination coverage.
- 2. To evaluate a pharmacy-based strategy for recruiting participants for a patient-reported active adverse event following immunization surveillance system.

Primary Hypothesis:

 Vaccine coverage with all studied vaccines will increase significantly after implementation of the bundled pharmacist-delivery strategy. A significant increase will be defined as an increase of ≥10% vaccine coverage from pre-program levels.

Secondary Hypotheses:

1. The cost of a vaccine is a key factor in an individuals' decision-making

ROMEO File #: 1021559

with respect to vaccination. It is expected that vaccinations provided at no or minimal charge will have higher uptake than those that require more financial resources to obtain.

2. We hypothesize knowledge about the vaccines studied, high dose TIV, meningococcal B vaccine, meningococcal ACWY vaccine, and Tdap, is low among the general public, but high among practitioners. We hypothesize we will find a high level of support among both the public and health care providers for pharmacists to provide vaccines measured in our study. Knowledge and support amongst both providers and the public will increase after implementation of the program.

Study Methodology

design

This will be a two-year demonstration program implementation and evaluation project in two Canadian provinces, New Brunswick and Nova Scotia. One community in each province will be allocated to implementation strategies specifically designed for each of the target vaccines. One community in each province will serve as the non-intervention control arm where pharmacist immunization practice will continue unchanged.

Inclusion criteria for the selection of the four communities are a stable population, service by a regional hospital and community pharmacies, and lack of substantial health care spill-over to adjacent communities. Spill over is defined as a pattern of health-care utilization where patients regularly receive care at different regional health centres. Communities will be geographically separated to minimize potential spill over.

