Vaccine coverage (number vaccinated divided by the number eligible for vaccine) will be measured using pharmacy database analysis, public health vaccine reports by physicians, vaccine doses delivered (in all four regions), and by public survey within the study communities (part of the KABB survey). Statistics Canada census data from 2015 will be used to determine the denominator for those eligible for the vaccine by 5-year age groups.

3. Adverse Events Following Immunization Reporting (AEFI)

Using the Canadian National Vaccine Safety Network (CANVAS)'s surveillance system for adverse events following seasonal influenza vaccination, we will compare the proportions of eligible individuals who register for CANVAS and complete the online AEFI survey among pharmacies using active recruitment strategies (e.g., handing out information sheets and registration forms) and those using passive recruitment strategies (e.g., displaying posters and information sheets).

Sample Size
 There are four communities involved in the study, Saint John and Moncton, New Brunswick and New Glasgow/Pictou/Antigonish and Kentville/Wolfville/New Minas, Nova Scotia. All participating pharmacies in each community will be allocated either to the bundled pharmacist-delivery intervention or to standard care (control arm). Residents in each community will receive a KABB survey, regardless of whether or not they were vaccinated as part of this study. Information and registration forms

ROMEO File #: 1021559

for CANVAS surveillance will be actively distributed to those who received influenza vaccines in the intervention communities and information on CANVAS will be displayed at pharmacies in control communities. A sample size of 400 for the KABB survey will provide a margin of error of less than 5% for estimated proportions. For vaccine coverage, a separate sample size of 596 per group will provide power of at least 80% to detect superiority.

Endpoints Outcomes/analysis plan/sample size/statistics Outcomes

- 1. Population-specific vaccine coverage before and after programimplementation interventions.
- 2. Proportion of population in intervention districts whose supplementary health benefit plans cover studied vaccines.
- 3. Public KABB about vaccine-preventable diseases and related vaccines before and after program-implementation interventions.
- 4. Public willingness to pay and co-pay for studied vaccines.
- 5. Healthcare providers KABB regarding pharmacist- delivered vaccine programs.

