2.2 Secondary Objectives

- 1. To assess the impact of various funding models on vaccination coverage.
- 2. To evaluate a pharmacy-based strategy for recruiting participants for a patient-reported active adverse event following immunization surveillance system.

2.3 Primary Hypothesis:

 Vaccine coverage with all studied vaccines (high dose TIV, meningococcal B vaccine, meningococcal ACWY vaccine, Tdap, herpes zoster vaccine, and travel health vaccines) will increase significantly after implementation of the bundled pharmacist-delivery strategy. A significant increase will be defined as an increase of ≥10% vaccine coverage from preintervention levels.

2.4 Secondary Hypotheses:

- 1. The cost of a vaccine is a key factor in the individual's decision to be vaccinated. It is expected that vaccinations provided at no or minimal charge will have higher uptake than those that require more financial resources to obtain.
- 2. Knowledge about the vaccines studied is low among the general public, but higher among practitioners. There is a high level of support among both the public and health care providers for pharmacists as immunizers. Knowledge and support amongst both providers and the public will increase after implementation of the program.

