Based on this inclusion criteria, four communities were selected. Intervention communities in which the communication and payment strategies will be implemented are: Saint John, New Brunswick and New Glasgow/Pictou/Antigonish, Nova Scotia area, which include the smaller towns of Stellarton and Westville, Nova Scotia. Control communities where pharmacy delivered immunizations will be offered under their current model are: Moncton, New Brunswick and Kentville/New Minas/Wolfville, Nova Scotia, which include the smaller towns of Canning and Coldbrook, Nova Scotia. Intervention and control communities will be compared to one another to assess the effectiveness of the bundled strategies.

Payment mechanisms will be applied in intervention communities, excluding no client from this strategy. Communication strategies will be targeted based on the type of vaccine a client is eligible to receive. Pharmacists will contact clients over the age of 65 by phone or mail out to recommend high-dose TIV and contact clients who are 50 and older to recommend herpes zoster. Clients who are immunosuppressed may also receive phone calls/mail outs for vaccines against meningococcal disease. Individual eligibility will also be assessed by pharmacists during consultations. Through client's interaction to fill prescriptions, pharmacists have regular contact with high-risk individuals and are able to proactively and systematically review patients' medical histories and medications to remind them of the benefits of specific vaccinations. They can also implement awareness campaigns during travel season and school breaks to target clients who may be travelling to high-risk areas and should consider getting vaccinated to protect themselves against travel-related illnesses, such as Hepatitis A and Typhoid Fever.

Measurement of vaccine coverage

Vaccine coverage rates will be measured using the following:

- **1.** pharmacy database analysis,
- 2. public health vaccine reports by physicians,
- 3. number of vaccine doses delivered to pharmacies in all four regions, and
- 4. public survey within the study communities to determine immunization status.

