
2. AEFI Surveys. Point estimates and exact binomial 95% confidence intervals will be calculated for the proportion of influenza vaccine recipients who register for the AEFI survey and the proportion who complete the survey. Descriptive statistics will be used to compare proportions registering and completing the survey among intervention versus control communities. Overall frequency of severe adverse events and the frequency of specific health events (e.g., injection site pain that prevents daily activities) will be calculated. The frequency of severe AEFI will be compared by influenza vaccine type [e.g., QIV, TIV] and by season (i.e., 2016-17 and 2017-18). The frequency of health events after vaccination will be compared to the background event rate estimated by the control survey.

3. Vaccine coverage. Pharmacy databases will be used to determine the number of doses administered to individuals eligible for receipt of vaccine relative to the total number of clients in the pharmacy database in the eligible age range. A second estimate of coverage will be

ROMEO File #: 1021559

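### Active versus passive AEFI recruitment is assigned by community together with the vaccine bundle, so the arm difference is bundle plus recruitment mode, and the exact binomial intervals ignore clustering by pharmacy and community

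*Combined protocol and SAP*

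**What the plan says.** Section 2.2 gives the second secondary objective: "To evaluate a pharmacy-based strategy for recruiting participants for a patient-reported active adverse event following immunization surveillance system". Outcome measure 3 in the synopsis describes the comparison as one "among pharmacies using active recruitment strategies" and those using passive ones.

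Allocation is by community. The synopsis says of the vaccine programme: "One community in each province will be allocated to implementation strategies specifically designed for each of the target vaccines"; the other community in each province is the control. Its sample-size paragraph confirms that "There are four communities involved in the study". Section 3.3 then assigns recruitment along the same line. For one arm: "In the intervention communities, vaccine recipients will be given an information sheet describing the survey and the CANVAS registration form". For the other: "In the control communities, recruitment will be passive". The registration route differs too: form or online in the intervention communities, online only in the control communities.

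For the analysis, section 6.2 (item 2, AEFI Surveys) says: "Point estimates and exact binomial 95% confidence intervals will be calculated for the proportion of influenza vaccine recipients who register for the AEFI survey". Completion is handled in the same way. The two arms are then compared by descriptive statistics. The only allowance for dependence in section 6.2 is under item 3 (vaccine coverage), and it concerns families.

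The objective is secondary in section 2.2, yet the registration and completion proportions appear under Primary Outcomes in section 6.1.1.

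**The concern.** There are two separate problems.

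**Aliasing.** No pharmacy within a community is assigned a different recruitment mode from its neighbours, so recruitment mode, vaccine bundle and community cannot be told apart. The bundle also acts on the people who form the AEFI denominator. In section 3.1, for the intervention communities only: "Pharmacists will contact clients over the age of 65 by phone or mail out to recommend high-dose TIV". Outreach of this kind can change the age mix of influenza vaccine recipients and their engagement with the pharmacy. The AEFI survey is sent by email, so age mix could plausibly affect registration and completion. No adjustment for recipient mix, pharmacy or province is planned.

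**Intervals.** Sheets and forms are handed out at the pharmacy counter, so registration is likely to vary with how consistently each pharmacy does it. An exact binomial interval has no term for that variation.

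At stake is what can be said about objective 2. A higher registration proportion in the intervention arm could be reported, with a tight interval, as evidence that active recruitment works, when the design supports neither the attribution nor the precision.

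**Working it through.** **1. The plan's own figures.** The plan states no sample size, correlation or precision for the AEFI comparison. Its one clustering allowance, for coverage in section 6.2 item 3, reproduces. Two adults per family with full concordance give a design effect of 1 + (2 − 1) × 1 = 2, so 298 × 2 = 596 and 1209 × 2 = 2418, as stated. The plan thus uses this reasoning for coverage and families, but not for AEFI recruitment, pharmacies or communities.

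**2. Aliasing.**

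| | Intervention communities (2) | Control communities (2) |
|---|---|---|
| Communication and payment bundle | yes | no |
| CANVAS recruitment | active | passive |
| Registration route | form or online | online only |

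The rows change together in every community. No contrast among the four communities isolates the second row.

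**3. Pharmacy as cluster.** Assumed inputs, not in the documents: m recipients per pharmacy and intra-pharmacy correlation ICC. Formulas: DE = 1 + (m − 1) × ICC; coverage of a nominal 95% interval = 2Φ(1.96/√DE) − 1.

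| m | ICC | DE | √DE | Actual coverage |
|---|---|---|---|---|
| 50 | 0.01 | 1.49 | 1.22 | 89% |
| 100 | 0.01 | 1.99 | 1.41 | 84% |
| 100 | 0.02 | 2.98 | 1.73 | 74% |
| 100 | 0.05 | 5.95 | 2.44 | 58% |
| 100 | 0.10 | 10.90 | 3.30 | 45% |
| 200 | 0.05 | 10.95 | 3.31 | 45% |

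Illustration, also assumed: with 10% registration among 2000 recipients in an arm (20 pharmacies × 100), the exact binomial half-width is 1.3 percentage points. Multiplied by √DE it becomes 2.3 points at ICC 0.02 and 3.3 points at ICC 0.05.

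**4. Community as cluster.** With 1000 recipients per community (assumed), DE = 1 + 999 × ICC, which is 2.0 at ICC 0.001 and 11.0 at ICC 0.01. Four communities in two arms leave 4 − 2 = 2 degrees of freedom. The critical value is then 4.30 instead of 1.96, a further factor of 4.30/1.96 = 2.2 for any between-arm interval.

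**5. Is a positive correlation plausible?** The background trial of pharmacist influenza vaccination in section 1.6 reports community means and SDs of 56.9% (28.0) and 80.1% (18.4). Crude correlations, SD²/[p(1 − p)], are 0.28²/(0.569 × 0.431) = 0.32 and 0.184²/(0.801 × 0.199) = 0.21. They are upper values, because the SDs include sampling error, and they concern coverage in another setting. They show that community variation can be large, but give no value for registration.

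**The case against.** Much of the case on the other side stands.

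- **Pharmacies as fixed.** The denominators are counts of influenza recipients in each community, taken from pharmacy databases. If the target is only the registration proportion in these pharmacies, differences between them add no sampling variance, and a binomial interval is valid or slightly conservative when recipients are otherwise independent. A reader might infer that the intervals simply fail to reach 95% coverage; that goes too far. The shortfall applies when the result is carried to other pharmacies. Evaluating a recruitment strategy does require that step.
- **No formal test.** A reader might infer an inflated false-positive rate. The plan names no test and no interval for the difference between arms on this item, so it commits to no such error. A descriptive difference is just as confounded, however.
- **Synopsis against section 3.3.** The pharmacy wording in outcome measure 3 might be read as a contradiction of the allocation. It is not: the synopsis sample-size paragraph also describes active distribution in intervention communities and display in control communities. The wording only makes the contrast look cleaner than it is.
- **Size of the confounding.** This is not shown. The outreach on high-dose TIV concerns clients over 65, whereas AEFI eligibility starts at 18. The documents do not allow the resulting shift in registration to be estimated.
- **Timing.** The AEFI seasons named are 2016-17 and 2017-18, and the protocol is dated 18 May 2021. Re-allocation cannot be applied to seasons that are past.

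**Conclusion.** The concern holds in two parts. First, the intervention-versus-control difference in registration and completion estimates bundle plus recruitment mode. This follows from the allocation alone and needs no assumption; its size cannot be derived from the documents. Second, for inference beyond these pharmacies, the exact binomial intervals are too narrow if the intra-cluster correlation is positive. With an assumed 100 recipients per pharmacy and ICC of 0.02 to 0.05, the design effect is 3.0 to 6.0 and actual coverage about 74% to 58%. Across 50 to 200 recipients and ICC 0.01 to 0.05, coverage runs from 89% to 45%.

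The matter touches a secondary objective with a descriptive comparison, so it does not threaten the trial as a whole. It does change what may be concluded on objective 2, and it should be corrected.

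**What to change.** **Analysis (section 6.2, item 2).** Replace the exact binomial intervals with cluster-aware ones, from pharmacy-level proportions or a pharmacy-clustered model. Report results by community within province. A pharmacy-clustered model alone does not deal with assignment by community, so state that two communities per arm leave very few degrees of freedom for the between-arm contrast.

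**Wording.** In synopsis outcome measure 3, section 3.3 and section 6.2 item 2, describe the contrast as bundle plus active recruitment versus standard care plus passive recruitment. Do not credit a difference to recruitment mode.

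**Data needed.** Registrations must be traceable to a pharmacy. The fields listed in section 3.3 (first name, vaccine and date, email, telephone) include no pharmacy, and vaccine provider is asked only in the later survey, so only of those who respond. A pharmacy code on the form and in the online registration would suffice. If none was collected, give community-level results and state that the intervals assume independence.

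**Only if a future season is still open.** Randomise pharmacies within the intervention communities to active or passive recruitment, and use the within-community comparison for secondary objective 2. The downsides are fewer actively recruited registrants and possible spill-over between pharmacies.

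**Cost.** The analysis and wording changes cost some text and wider intervals. The pharmacy code is a small addition to data collection.

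### AEFI frequencies pool actively and passively recruited registrants, with no stated limit on registering after a reaction, so post-vaccination event rates may be inflated by an unknown amount

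*Combined protocol and SAP*

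**What the plan says.** Section 3.3 sets up two recruitment modes. In intervention communities "vaccine recipients will be given an information sheet describing the survey and the CANVAS registration form", and "Participants will be asked to complete the registration form or to register online". In control communities "recruitment will be passive (e.g., posters and information sheets will be displayed) and potential participants will be required to register online".

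Both modes feed a "specific survey of adverse events experienced during the first 7 days following vaccination". The only timing rule concerns the questionnaire: "The AEFI survey will be emailed to registered participants on day 8 post-vaccination". The details requested at registration are "first name, vaccine received and date of vaccination, email address, and telephone number"; the date of registration is not among them.

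For analysis, section 6.2 states: "Overall frequency of severe adverse events and the frequency of specific health events (e.g., injection site pain that prevents daily activities) will be calculated". It adds: "The frequency of severe AEFI will be compared by influenza vaccine type", and also by season. Post-vaccination frequencies are then set against a background rate from a second survey of the same registrants, which section 3.3 schedules shortly before the following season's campaign. The only contrast planned between intervention and control communities is of the proportions registering and completing. Section 7 sets up no monitoring committee and refers to the AEFI surveys for safety monitoring.

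**The concern.** If a person can react first and register second, the outcome influences who enters the sample. Registration that needs more initiative, such as going online after seeing a poster, plausibly draws a higher proportion of people with something to report. Three planned outputs are exposed.

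- **Overall frequency.** It mixes two recruitment streams that may be selected to different degrees.
- **Background comparison.** The control survey covers a week long after registration. Reaction-prompted registration can raise the post-vaccination rate but cannot raise the background rate in the same way, so the comparison is asymmetric in both arms.
- **Vaccine-type comparison.** Under section 3.1, the high-dose TIV co-pay and the outreach to clients over 65 apply only in intervention communities, where recruitment is active. If product mix differs by community, vaccine type is partly confounded with recruitment mode.

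The stated secondary objective is recruitment, but these frequencies are explicit outputs and, given section 7, are the study's main safety information.

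**Working it through.** The plan gives no AEFI rate, registration rate or AEFI sample size, so there is no figure to reproduce. The check has two parts.

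**1. Can selection on the outcome occur?** The event window is days 0 to 7 and the survey goes out on day 8. Neither 3.3 nor 6.2 requires registration at the visit or before symptom onset. Intervention recipients may use the paper form or the website; control recipients have only the website. Late registration is therefore possible in both arms. No stratification, restriction or sensitivity analysis by mode or registration time is stated.

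**2. How large could it be?** All inputs here are assumptions:

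- p = true event rate, 3%
- k = how many times as likely a person with an event is to register, compared with a person without one
- w = share of respondents recruited passively

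Rate observed within a stream = kp / (1 + (k − 1)p):

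- k = 1: 3.0%
- k = 2: 0.06/1.03 = 5.8%
- k = 3: 0.09/1.06 = 8.5%
- k = 5: 0.15/1.12 = 13.4%

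Pooled rate = (1 − w) × active rate + w × passive rate. With no selection in the active stream, the pooled rate (and its ratio to 3%) is:

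| w | passive k = 2 | passive k = 3 | passive k = 5 |
|---|---|---|---|
| 5% | 3.14% (1.05) | 3.27% (1.09) | 3.52% (1.17) |
| 10% | 3.28% (1.09) | 3.55% (1.18) | 4.04% (1.35) |
| 25% | 3.71% (1.24) | 4.37% (1.46) | 5.60% (1.87) |
| 50% | 4.41% (1.47) | 5.75% (1.92) | 8.20% (2.73) |

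*Mild selection in the active stream too.* With k = 1.25 there, the active rate is 0.0375/1.0075 = 3.7%. With passive k = 3, the passive stream's share of the pooled inflation is w(8.49 − 3) / [w(8.49 − 3) + (1 − w)(3.72 − 3)]. This gives 29%, 46%, 72% and 88% at w = 5%, 10%, 25% and 50%.

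*Vaccine type.* Suppose two types have the same true rate of 3%, but 40% of one type's respondents and 10% of the other's are passive. With k = 2 the ratio of observed rates is (0.6 × 3 + 0.4 × 5.83) / (0.9 × 3 + 0.1 × 5.83) = 4.13/3.28 = 1.26. With k = 5 it is 7.16/4.04 = 1.77.

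*Background.* If the background rate carries no such selection, the ratio of post-vaccination to background frequency is multiplied by the factors in the table.

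**The case against.** The strongest defence is that this component exists to evaluate recruitment. The listed AEFI outcome in 6.1.1 is the proportions registering and completing, which are not damaged, and no event-rate contrast between communities is planned. That limits the weight of the point but does not remove it, because 3.3 and 6.2 still commit to the frequencies and comparisons.

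The study also uses an existing surveillance platform whose registration form is not reproduced, and the appendices are withheld. A cut-off might exist there, so the gap is established only for the text available.

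A reader might infer more than the documents support:

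- **That rates are inflated.** No evidence is given that symptoms drive registration; with k = 1 the inflation is nil.
- **That intervention registrants all enrol at vaccination and the bias sits mostly in control communities.** Section 3.3 lets intervention recipients register online as well, with no time limit. The passive stream's contribution to the pooled rate depends on its share, which may be small.
- **That the within-stream figures, such as 8.5% or 13.4%, are the error in the reported result.** They apply to passive registrants alone; the pooled effect is smaller.
- **That high-dose TIV will look falsely safer.** The planned comparison gives QIV and TIV as examples and does not name high-dose. Outreach for high-dose is aimed at people over 65, so age is a further confounder.

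**Conclusion.** The concern holds as an unaddressed risk of upward selection, not as a demonstrated bias. Post-vaccination event rates may be inflated in both arms, plausibly more per registrant under passive recruitment. The background comparison is asymmetric by design, and the vaccine-type comparison is confounded with mode if product mix differs by community.

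On the assumed inputs (true rate 3%, passive selection 2 to 5 times, passive share 5 to 50%, no selection in the active stream), pooled inflation runs from about 1.05- to 2.7-fold. It is small if few people register passively. The stated analyses would not show which case applies. The point is secondary in importance but cheap to address.

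**What to change.** In section 6.2:

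1. Report AEFI frequencies by recruitment mode. Community defines mode and is already needed for the registration comparison.
2. Make the vaccine-type comparison within mode or stratified by it, and acknowledge age as a further confounder.
3. Where the registration date is available, add a sensitivity analysis with one fixed window for everyone: registered on the day of vaccination or the next day. A same-day reaction can still prompt registration, so this reduces the problem without removing it.
4. Use symptom onset only to describe how many events preceded registration. It should not be an inclusion rule: onset is asked only of people reporting severe or medically attended symptoms, so a rule based on it selects on the outcome. For example, assume a true rate of 5%, everyone registering on day 3 and 70% of onsets already past. Dropping those cases leaves 1.5 events among 96.5 people, or 1.6%.
5. State symptom-prompted registration as a limitation of the background comparison.
6. Keep all registrants for the registration and completion proportions.

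The cost is analysis-plan wording, smaller strata and less precise rates. The availability of registration dates must be confirmed first: they are not among the listed items, and the AEFI seasons (2016-17 and 2017-18) precede this May 2021 protocol, so dates not captured then may not be recoverable. Items 1, 2, 5 and 6 do not depend on them.
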